3.5.2 Discontinuation Guidelines due to sustained elevated Serum Creatinine

Subjects will have double blind study medication withheld and a confirmatory, repeat S_{Cr} drawn within one week, if the following criterion is met:

• Male or female subjects: $S_{Cr} \ge 2.0 \text{ mg/dL} (176 \mu \text{mol/L})$

The following actions should be taken upon receipt of the central laboratory repeat SCr result:

- If the repeat S_{Cr} is < 2.0 mg/dL (176 μ mol/L), double-blind study medication may be resumed unless otherwise contraindicated.
- If the repeat S_{Cr} is $\geq 2.0 \text{ mg/dL}$ (176 μ mol/L), the subject must be immediately discontinued from the study, the Sponsor notified, and the Day 14 visit performed. The Investigator will follow the subject until the event has resolved or stabilized.

3.5.3 Discontinuation Guidelines due to Sustained Elevated liver Safety Abnormalities

The monitoring for liver safety will be performed using the serum levels of AST, ALT and total bilirubin (TB) (see Appendix 4 for algorithm flow chart). Subjects with central laboratory ALT and/or AST > 3 X ULN will be scheduled for a follow-up visit within 3 days following receipt of the initial laboratory results, to obtain repeat central laboratory ALT, AST, TB and Alkaline Phosphatase (ALK-P). In the event that the repeat laboratory assessments cannot be obtained within 3 days, the Investigator is encouraged to discuss possible alternatives with the Sponsor. Subjects should remain on study medication until confirmatory results are obtained, unless otherwise contraindicated.

dapagliflozin	MB102072
BMS-512148	Clinical Protocol

- If the repeat ALT and AST are ≤ 3X ULN, subject should continue in the double blind treatment period according to their original visit schedule unless otherwise contraindicated.
- If the repeat ALT and/or AST are > 3X ULN but ≤ 8X ULN and TB ≤ 1.5X ULN, the subject's medical history, including details of risk factors for liver diseases, should be evaluated for potential underlying etiologies. In addition, specialized blood sampling will be performed to evaluate liver function as well as identify potential causes of laboratory elevation(s). The Investigator should continue to monitor the subject's liver tests every 3 days following receipt of the prior laboratory results until the ALT and AST are ≤ 2X ULN or until ALT and AST are at or below baseline levels. The frequency of retesting can decrease to once a week or less if abnormalities stabilize and the subject is asymptomatic. Subjects should remain on study medication unless confirmatory results indicate that a criterion for discontinuation has been met or continuing study medication would be otherwise contraindicated.

Subjects must be discontinued from the study medication if an initial and repeat confirmatory laboratory tests meet any of the following criteria:

- ALT and/or AST are > 3X ULN and TB > 1.5X ULN
- ALT and/or AST are > 5X ULN for \ge 14 consecutive days, at any time after initial confirmatory results
- ALT and/or AST are > 8X ULN

In each of these situations, study medication will be discontinued, the Sponsor notified and the Day 14 visit performed within 3 days of the confirmed laboratory results. At the Day 14 visit, medical history including details of risk factors for liver diseases (if not previously assessed) will be requested and additional blood sampling performed (see Section 5.3.3 and Appendix 2). A referral consultation to a hepatologist or gastroenterologist (specializing in liver abnormalities) should be obtained.

Following the Day 14 visit, the Investigator should continue to monitor the subject's liver tests every 3 days following receipt of the prior laboratory results until the ALT and AST are $\leq 2X$ ULN or until ALT and AST are at or below baseline levels. The frequency of retesting can decrease to once a week or less if abnormalities stabilize and the subject is asymptomatic (see Appendix 4).

dapagliflozin	MB102072
BMS-512148	Clinical Protocol

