- d) Any unstable endocrine, psychiatric, rheumatic disorders as judged by the Investigator.
- e) Subject is, in the judgment of the Investigator, unlikely to comply with the protocol or has any severe concurrent medical or psychological condition that may affect the interpretation of efficacy or safety data.
- f) Subject with any condition which, in the judgment of the Investigator, may render the subject unable to complete the study or which may pose a significant risk to the subject.
- g) Subject is currently abusing alcohol or other drugs or has done so within the last 6 months.
- h) Subject is a participating investigator, study coordinator, employee of an investigator or immediate family member of any of the aforementioned.

dapagliflozin	MB102072
BMS-512148	Clinical Protocol

- i) Previous participation in a clinical trial with dapagliflozin (BMS-512148) and/or with any other SGLT2 inhibitors.
- j) Administration of any other investigational drug within 30 days of planned enrollment to this study.
- k) No clinical conditions or clinically significant abnormalities, in any laboratory value(s) collected after screening and prior to randomization which, in the Investigator's judgment, should preclude entry into the treatment period

Eligibility criteria for this study have been carefully considered to ensure the safety of the study subjects and to ensure that the results of the study can be used. It is imperative that subjects fully meet all eligibility criteria.

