3.5 Discontinuation of Subjects from Treatment

Subjects MUST discontinue investigational product (and noninvestigational product at the discretion of the investigator) for any of the following reasons:

- Withdrawal of informed consent (subject's decision to withdraw for any reason)
- Any clinical adverse event (AE), laboratory abnormality or intercurrent illness which, in the opinion of the investigator, indicates that continued participation in the study is not in the best interest of the subject
- Pregnancy
- Termination of the study by Bristol-Myers Squibb (BMS)
- Loss of ability to freely provide consent through imprisonment or involuntary incarceration for treatment of either a psychiatric or physical (eg, infectious disease) illness

dapagliflozin	MB102072
BMS-512148	Clinical Protocol

- Protocol-defined major hypoglycemia episode or recurrent non-major hypoglycemia episodes (see Section 3.5.1)
- Sustained elevated S_{Cr} (see Section 3.5.2)
- Sustained elevated liver safety abnormalities (see Section 3.5.3)
- Sustained hyponatremia (see Section 3.5.4).
- Sustained elevated CK (see Section 3.5.5)

All subjects who discontinue should comply with protocol specified follow-up procedures for Day 14/ET visit as outlined in Section 5.1. The only exception to this requirement is when a subject withdraws consent for all study procedures or loses the ability to consent freely (ie, is imprisoned or involuntarily incarcerated for the treatment of either a psychiatric or physical illness).

If a subject was withdrawn before completing the study, the reason for withdrawal must be entered on the appropriate case report form (CRF) page.

3.5.1 Discontinuation Guidelines due to Protocol-Defined Major Hypoglycemia Episode or Recurrent Non-Major Hypoglycemia Episodes

Subjects will be discontinued from study medication if they experience severe and/or frequent hypoglycemia episodes, defined as 1 major episode or recurring non-major episodes in the event where the possibility of down-titration of contributing concomitant medication(s) (other than double-blind study medication), and/or other contributing factors (eg, excessive physical activity) have been evaluated and corrected. NOTE: Dose titration of double-blind study medication is not permitted at any time during the treatment period.

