Review Insulin/diary data			Х	Х	Х	Х	Х	Х	Х	Х	Х			
Adjustment of Insulin, as needed		Х	Х	Х	Х	Х	Х	Х	Х	Х	Х			
SAFETY ASSESSMENT														
Assess Adverse Events		Х	Х	Х	Х	Х	Х	Х	Х	Х	Х			
Assess Hypoglycemia episodes		Х	Х	X	Х	Х	X	X	Х	X	Х			

dapagliflozin BMS-512148

Procedure	Screen-			Inj	patient			Outpatient						
	ing*	Baseline				Dou	ıble-Blin	d Treat	ment		Follow-Up	Notes		
		Day -3	Day -2	Day -1	Day 1	Day 2 to 6	Day 7	Day 8	Day 10 ^a	Day 14/ET ^b	Day 21 ^c	*Day -3 should occur within 30 days of screening visit.		
Dispense Urine Ketone Dipstick & Training (as needed)		Х						Х	Х					
Subject Performs Urine Ketones (dipstick) daily (record in diary)		X	X	X	X	Х	X	X	Х	X		This will begin on day -2 if entry in afternoon or evening		
Review Urine Ketone Dipstick Results		X	Х	X	X	X	Х	X	Х	X	Х			
Record daily fluid intake and output		X	X	X	X	Х	X					This will begin on day -2 if entry in afternoon or evening		
Insert/calibrate CGMS		X				X (Day 4)		X		X		Data upload should occur at the time of the sensor change		

dapagliflozin
BMS-512148

Table 5.1.1:	Flow Cha	rt/Time	and E	Events	Schedu	le						
Procedure	Screen-		Inpatient							(Outpatient	
	ing*	Baseline				Dou	ıble-Blin	d Treat	ment		Follow-Up	Notes
		Day -3	Day -2	Day -1	Day 1	Day 2 to 6	Day 7	Day 8	Day 10 ^a	Day 14/ET ^b	Day 21 [°]	*Day -3 should occur within 30 days of screening visit.
CGMS data collection for PD assessments				X	X		X			X (day 13)	Х	Subjects will wear the device for the duration of the study and all data will be captured. Days marked indicate periods used for analysis by BMS.
SMBG -fingersticks- at least 4 x per day -before breakfast, lunch, dinner and bedtime (and as needed) including during outpatient period		X	X	X	X	X	X	X	X	X	X	Subjects should enter all valid SMBG values into the CGMS

dapagliflozin
BMS-512148

_

Table 5.1.1:	Flow Cha	art/Time	and E	Events	Schedu	le								
Procedure	Screen-			Inj	patient			Outpatient						
	ing*	Baseline				Dou	uble-Blin	d Treat	ment		Follow-Up	Notes		
		Day -3	Day -2	Day -1	Day 1	Day 2 to 6	Day 7	Day 8	Day 10 ^a	Day 14/ET ^b	Day 21 ^c	*Day -3 should occur within 30 days of screening visit.		
CENTRAL LABORATORY														
Pregnancy test (urine) WOCBP only	X		Х	Х					Х	X	Х			
Blood Standard Safety Laboratory Panel	Х		Х		Х		X			X	Х			
Urine Standard Safety Laboratory Panel	Х		X		Х		X			X	Х			
24-h urine collection for Glucose, Sodium, Uric Acid and Creatinine				Х	Х		Х							

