7-point central laboratory glucose monitoring (before and 2-hr after each meal [breakfast, lunch, dinner] as well as bedtime[~11 pm])				X	X		X							

dapagliflozin	
BMS-512148	

Table 5.1.1:	Flow Cha	rt/Time	and E	Events	Schedu	le						
Procedure	Screen-		In	patient			Outpatient					
	ing*	В	aseline			Dou	ıble-Blin	d Treat	ment		Follow-Up	Notes
		Day -3	Day -2	Day -1	Day 1	Day 2 to 6	Day 7	Day 8	Day 10 ^a	Day 14/ET ^b	Day 21 ^c	*Day -3 should occur within 30 days of screening visit.
FPG	X			X	Х		Х			X		
Fasting C-peptide	X											
Serum Insulin							Х					Day 7 Pre-dose, after lunch and after dinner
A1C	X											
Hepatitis Screen Panel/TSH	Х											
Fasting Serum Lipids	X						X			X		
FFA	X				X		X			X		
Serum β-hydroxybutyrate			X		X		X			X	X	

Date:

dapagliflozin
BMS-512148

Table 5.1.1:	Table 5.1.1:Flow Chart/Time and Events Schedule											
Procedure	Screen-	Inpatient					Outpatient					
	ing*	B	Baseline			Do	uble-Blin	d Treat	ment		Follow-Up	Notes
		Day -3	Day -2	Day -1	Day 1	Day 2 to 6	Day 7	Day 8	Day 10 ^a	Day 14/ET ^b	Day 21 ^c	*Day -3 should occur within 30 days of screening visit.
PK sample collection at 0 h 0.5,1,2,3,4,6,8,12, and 24 h post-dose							X	X				24 h post-dose PK sample occurs Day 8 for dose administered on Day 7.
DRUG DISPENSING												
Dispense Study Medication					X	X	X	X	X			The kit assigned to each subject on Day 1 for inpatient dosing will be the same kit each subject takes home on Day 8 for outpatient dosing.

dapagliflo	zin
BMS-512	148

Table 5.1.1:	Flow Cha	rt/Time	and E	Events	Schedu	le						
Procedure Screen- Ir				Inj	patient	atient Outpatient						
	ing*	B	aseline			Dou	uble-Blin	d Treat	ment		Follow-Up	Notes
		Day -3	Day -2	Day -1	Day 1	Day 2 to 6	Day 7	Day 8	Day 10 ^a	Day 14/ET ^b	Day 21 [°]	*Day -3 should occur within 30 days of screening visit.
Review Study Medication Compliance						Х	X	X	X	X		Subjects will be instructed to take 1 tablet from each of 3 bottles every day of the 14-day treatment period (including days 9 and 11-14).

^a Visit may be scheduled ± 1 day to allow flexibility of scheduling.

^b All subjects who discontinue should have day 14/early termination (ET) procedures as indicated here.IVRS should be called to record status (ie discontinuation). The Day 14/ET e CRF will need to be completed. The investigator should arrange appropriate follow-up care, as applicable. It is important for Day 14 to occur 14 days relative to/from first dose

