5.3.11 Guidance on Assessment of Hepatic Laboratory Abnormalities

An independent Hepatic Adjudication Committee, blinded to the treatment of the subjects, will determine the probability that drug-induced liver injury (DILI) is the cause of liver-related abnormalities, including, but not limited to:

- Hepatic disorders leading to discontinuation from study treatment and/or death
- Liver laboratory abnormalities such as elevated AST and/or ALT with or without TB elevations.

A separate Adjudication Manual will define and describe the procedure for the handling, reporting and classification of these cases.

dapagliflozin	MB102072
BMS-512148	Clinical Protocol

The following is presented to assist in the evaluation and management of hepatic laboratory values. It is not intended to supplant Investigators' clinical judgment.

Subjects who experience ALT and/or AST values > 3X ULN confirmed with a repeated test will have the following performed within 3 days of the confirmed laboratory results:

- AE assessment
- Physical Examination for jaundice and other signs of liver diseases
- Review of relevant risk factors and current history focusing on possible causes of the increased ALT and/or AST and/or TB, including:
 - Use of suspect concomitant medication [including over-the-counter (ie, acetaminophen/paracetamol), herbal and vitamin preparations]
 - Recent alcohol consumption or recreational drug/narcotic use
 - Recent unaccustomed physical exertion
 - Occupational or environmental exposure to hepatotoxins
 - Other conditions which may cause liver diseases or which may cause abnormal test results
- Specialized Liver Laboratory Panel (see Appendix 2)

Additional information, including but not limited to completion of supplemental eCRFs, may be requested for certain adverse events and/or laboratory abnormalities which are reported/identified as part of the hepatic safety surveillance.

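### In a 14-day study, the mandatory liver stop at ALT or AST above 5X ULN for 14 consecutive days cannot stop a dose for an elevation that arises on treatment

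*Protocol*

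**What the plan says.** Section 3.5.3 requires discontinuation when the initial and repeat tests meet any of three criteria:

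- ALT or AST above 3X ULN with total bilirubin (TB) above 1.5X ULN;
- ALT or AST above 5X ULN for at least "14 consecutive days, at any time after initial confirmatory results";
- ALT or AST above 8X ULN.

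While the repeat is awaited, the rule is: "Subjects should remain on study medication until confirmatory results are obtained, unless otherwise contraindicated". If the repeat lies above 3X and up to 8X ULN with TB at or below 1.5X ULN, causes are evaluated, specialized blood samples are taken and liver tests are repeated every 3 days. For this branch the section adds: "Subjects should remain on study medication unless confirmatory results indicate that a criterion for discontinuation has been met", or unless continuing is otherwise contraindicated.

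Two other sections bear on the same subjects. Section 3.5 makes stopping mandatory for any "laboratory abnormality or intercurrent illness which, in the opinion of the investigator, indicates that continued participation" is against the subject's interest. Section 5.3.11 states: "Subjects who experience ALT and/or AST values > 3X ULN confirmed with a repeated test will have the following performed within 3 days", and lists AE assessment, physical examination, risk-factor review and a specialized liver panel. It also sets up a blinded Hepatic Adjudication Committee.

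On timing, Table 5.1.1 has subjects take tablets "every day of the 14-day treatment period (including days 9 and 11-14"), and Day 14 is fixed relative to the first dose. The row "Blood Standard Safety Laboratory Panel" is marked at screening and on Days -2, 1, 7, 14 and 21.

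**The concern.** The duration in the second criterion is as long as the whole treatment period. An elevation has to appear before it can persist, so one that begins on drug should outlast dosing before the criterion is met. The band above 5X and up to 8X ULN with TB at or below 1.5X ULN would then be governed by the continue branch alone.

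The other laboratory stops work differently. Creatinine (3.5.2), sodium (3.5.4) and creatine kinase (3.5.5) all withhold drug at the first threshold value and decide on a short repeat.

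At stake are the doses that an affected subject takes after detection, in the first study of this drug in type 1 diabetes, where safety is the primary objective. A site or ethics committee reading the list would also credit the protocol with a dose stop that it does not have in practice.

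**Working it through.** The plan gives no figure of its own for this rule, so the check is a day count.

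Inputs:

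- Required duration: 14 consecutive days (3.5.3).
- Last dose: Day 14 (Table 5.1.1).
- Liver panels: screening, Days -2, 1, 7, 14 and 21 (Table 5.1.1).
- Samples are taken fasting in the morning (Appendix 2) and the dose is taken with the morning meal (4.3). The Day 1 panel is therefore pre-dose, and the Day 7 dose is normally taken before any Day 7 result is known.
- Repeat test: within r = 0 to 3 days of receiving the first result (3.5.3).
- Central-laboratory turnaround t: not in the protocol; 0 to 3 days is assumed.

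**Step 1: when the criterion is met.** For a first high sample on Day d after the start of dosing, the 14th day is d + 13 if the sample day counts, or d + 14 if 14 days must elapse. The study has no Day 0, so from Day -2 the dates are Day 12 and Day 13.

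| First sample above 5X ULN | Met, inclusive count | Met, elapsed count | Doses left after that day |
|---|---|---|---|
| Day -2 (pre-dose) | Day 12 | Day 13 | 2 or 1 |
| Day 1 (pre-dose) | Day 14 | Day 15 | 0 |
| Day 2 (unscheduled) | Day 15 | Day 16 | 0 |
| Day 7 | Day 20 | Day 21 | 0 |

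The Day -2 row assumes same-day results. In the Day 1 row, the Day 14 dose could be spared only if that morning's sample were read before the tablet was taken. If the clock starts at the confirmatory result, every date is later.

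The first two rows need a subject who passed the entry limit of 2X ULN at screening and was still randomized with a high value. That is possible, because exclusion 6k covers abnormalities "in any laboratory value(s) collected after screening and prior to randomization which, in the Investigator's judgment, should preclude entry" and so leaves the decision to judgment.

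**Step 2: doses remaining.** After the Day 7 panel: 14 - 7 = 7 (Days 8 to 14). The confirmatory result arrives on Day c = 7 + t + r + t, and the doses left are max(0, 14 - c).

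| Turnaround t (assumed) | Confirmatory result | Doses left |
|---|---|---|
| 0 days | Day 7 to 10 | 4 to 7 |
| 1 day | Day 9 to 12 | 2 to 5 |
| 2 days | Day 11 to 14 | 0 to 3 |
| 3 days | Day 13 to 16 | 0 to 1 |

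The last column is also what a stop on two values above 5X ULN would spare. For an elevation arising on treatment, the present criterion spares none.

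**Step 3: effect of one extra stop on the primary endpoint.** With 14 subjects per arm (8.1), one more discontinuation adds 1/14 = 7.1 percentage points to endpoint 1d in that arm.

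**The case against.** The strongest reply is that nothing fails. The criterion tolerates up to 14 days in this band, dosing ends before that tolerance is used up, and so no subject with an on-treatment elevation is dosed beyond what the rule allows. Section 3.5.3 deliberately puts these subjects in a work-up-and-continue branch, and no text shows that a shorter tolerance was meant. This stands in part: the replacement is a stricter clinical threshold, and choosing it belongs to the sponsor's safety physicians. It does not answer the narrower point that a listed mandatory stop cannot perform its dose-stopping function.

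Four stronger readings are tempting, and the documents do not support them.

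- A reader might infer that these subjects are unprotected. The investigator must stop drug when continuation is judged against the subject's interest. Retesting every 3 days also feeds the two stops without a duration, so a worsening subject is caught.
- A reader might infer that the criterion is wholly inert. Liver tests continue until values settle, and a Day 21 panel is scheduled. A criterion met on Day 20 or 21 could still prompt sponsor notification and specialist referral.
- A reader might take 7 doses as the exposure after confirmation. That needs zero turnaround and a same-day repeat.
- A reader might infer that the bullet came from a longer study, since Appendix 2A names visits at Weeks 4 to 13 that this study lacks. The protocol does not say so, and the point does not depend on it.

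**Conclusion.** The point holds as a minor safety matter. For an elevation that arises on treatment, the 14-day criterion cannot stop a dose under either way of counting. It can be met on a dosing day only if the elevation was already present on Day -2 or Day 1. In the band above 5X and up to 8X ULN with TB at or below 1.5X ULN, continuing is the written default and stopping rests on each investigator's judgment.

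The size is modest: 7 doses per affected subject is a ceiling, and after confirmation there are usually fewer. The day counts rest on the protocol alone; the dose ranges after confirmation rest on the assumed turnaround. The number of affected subjects cannot be derived from the protocol. It is likely to be small, because ALT or AST above 2X ULN, positive hepatitis B or C screens and significant hepatic disease are excluded at entry.

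**What to change.** In Section 3.5.3, replace the second bullet with: ALT and/or AST > 5X ULN on both the initial test and the confirmatory repeat. The sponsor's safety physicians should confirm the threshold.

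Then align the rest:

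- Lower the upper limit of the continue branch from 8X to 5X ULN in Section 3.5.3 and in Appendix 4 footnote a, with any matching flow-chart step (the chart itself could not be checked).
- Say that a repeat above 5X ULN after a first value at or below 5X ULN is treated as a new initial value. Otherwise that subject falls between the two branches.
- Drop the > 8X ULN bullet, which becomes redundant, or recast it as a stop at the first value. Recasting also means exempting it from the initial-and-repeat condition and from the sentence that keeps subjects on drug until confirmation.

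The cost is low. The repeat within 3 days is already required, so no new scheduled sample is needed. The downside is an occasional earlier discontinuation after Day 7. It brings the Day 14 visit forward to within 3 days of the confirmed result and adds the liver discontinuation panel and a specialist referral. It is recorded as an AE under Section 6.3 and counts in endpoint 1d. Day 7 pharmacokinetic and 7-point glucose data are normally kept, because the Day 7 dose precedes any Day 7 result. With a turnaround of 2 to 3 days the gain may be nil for some subjects.

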3.5.4 Discontinuation Guidelines due to Hyponatremia

Subjects with a serum sodium $\leq 125 \text{ mEq/L} (125 \text{ mmol/L})$ will have double-blind study medication withheld and a confirmatory, repeat serum sodium, drawn within 3 days following receipt of the initial laboratory result.

- If the repeat serum sodium is $\geq 130 \text{ mEq/L} (130 \text{ mmol/L})$:
 - Double-blind study medication may be resumed unless otherwise contraindicated.
 - Serum sodium should be re-tested within one week after resuming the double blind study medication.
 - If the repeat of serum sodium, obtained within one week after resuming double-blind study medication, is < 130 mEq/L (130 mmol/L), the subject must be immediately discontinued from the study, the Sponsor notified and the Day 14/ET visit performed. The Investigator will follow the subject until the event has resolved or stabilized.
 - If the repeat of serum sodium, obtained within one week after resuming double-blind study medication, is ≥ 130 mEq/L (130 mmol/L), the subject may continue in the study and will be followed according to the protocol. Additional monitoring of serum sodium may be performed according to the local practice or Investigator's judgment.
- If the repeat serum sodium is < 130 mEq/L (130 mmol/L) **AND** there is no suspected new, temporary and reversible cause of hyponatremia based on clinical assessment (other than the administration of double-blind study medication), the subject must be immediately discontinued from the study, the Sponsor notified and the Day 14/ET visit performed. The Investigator will follow the subject until the event has resolved or stabilized.
- If the repeat serum sodium is < 130 mEq/L (130 mmol/L) **AND** there is a suspected new, temporary and reversible cause of hyponatremia based on clinical assessment (other than the administration of double-blind study medication):
 - Double-blind study medication will continue to be withheld.
 - The suspected cause of hyponatremia should be identified and corrected.
 - Serum sodium should be re-tested within one week after the first repeat:
 - If the repeat of serum sodium, obtained within one week after the first repeat, is < 130 mEq/L (130 mmol/L):
 - The subject must be immediately discontinued from the study, the Sponsor notified and the Day 14/ET visit performed. The Investigator will follow the subject until the event has resolved or stabilized.

dapagliflozin	MB102072
BMS-512148	Clinical Protocol

- If the repeat of serum sodium, obtained within one week after the first repeat, is $\geq 130 \text{ mEq/L} (130 \text{ mmol/L})$:
 - Double-blind study medication may be resumed unless otherwise contraindicated.
 - Serum sodium should be re-tested within one week after resuming double-blind study medication,
 - The subject may continue in the study and will be followed according to the protocol. Additional monitoring of serum sodium may be performed according to the local practice or Investigator's judgment.

For subjects whose serum sodium is between 126 and 129 mEq/L (126 and 129 mmol/L), the Investigator's clinical judgment should apply concerning whether such subjects should be followed according to the above algorithm (see Appendix 3 for algorithm flow chart).

